9.6.1 General restrictions and recommendations

9.6.1.1 General restrictions

- Contraception Requirements: All WOCBP must use effective contraception (defined in inclusion criterion #8) or practice abstinence from at least four weeks prior to first dose to four weeks after last dose. No contraception requirement for male subjects.
- Meals and Dietary Restrictions:

At the clinic:

Visit 2 (Day 1): Standardised breakfast at the clinic. Administration of a test placebo capsule (all treatment arms) during breakfast. Satiety and craving questionnaire before breakfast and then once every hour for 4 hours until just before lunch (at home).

Visit 3, 4 and 5 (Week 7, 14 and 26): Standardised breakfast at the clinic. IMP administration during breakfast. Satiety and craving questionnaire before breakfast (at the clinic) and then once every hour for 4 hours until just before lunch (at home).

CONFIDENTIAL 48 (92)

Clinical Study Protocol EP-002 Final version v3.0 12NOV2020

For details on IMP administration, refer to Section 10.5.

Standardised breakfast: A menu option (decided by CTC) will be offered while the patients are at the research clinic. The meal selection is standardised in the sense that the nutritional content of the meals should be similar at each time point of each treatment day.

At home:

The patients should take the IMP TID in association with the three main meals per day.

- Fasting: The patients should be fasting overnight (8 hours) before Visit 2 to Visit 5 and before Visit 7.
- Alcohol: Consumption of alcohol is not allowed from 24 hours prior to and during all visits to the clinic including Visit 7.
- Nicotine: A stable habit of smoking or use of nicotine-containing products is allowed, yet patients should not change their smoking pattern during the study from screening until Visit 6.
- Exercise: The patients must refrain from strenuous exercise (defined as greater than 70% of the maximal pulse rate for one hour or more) from 48 hours prior to and during all visits.
- Blood donation: The patients must not donate blood or plasma during the study until three months after the final medical examination at Visit 6.
- Participation in other clinical studies: Study patients are not allowed to participate in any other interventional clinical study within three months prior to the first administration of IMP in this study, and during the study until Visit 7.
- Accessibility: patients have access to a mobile phone or other electronic device for electronic diary assessments (ViedocMe).

9.6.1.2 Diet recommendations

The patient will be recommended to adhere to the Nordic Nutrition recommendations, so as to minimise risk for GI-related symptoms during treatment with EMP16-02.

Several study-specific clarifications will be made in relation to the Nordic Nutrition recommendations. These will also lead to a caloric deficit if followed:

- Limit meal size and eat slowly until sufficiently full
- Focus on vegetables that contain a high proportion of fibre, such as green peas, brussels sprouts, suede, salsify, kale, broccoli, Jerusalem artichoke and mushrooms.
- If temporarily problems with gastric distension and flatulence occur, choose "kinder" vegetables that contain a lower proportion of fibres, such as carrots, zucchini/squash, sweet potatoes, beets, parsnips.
- Choose sourdough bread, preferably baked with rye.
- Add psyllium husk to morning and evening meals, especially if you have loose stools.
- Choose muesli and porridge with a high amount of oats (must not be whole-bran oats).
- Eat fruits and berries, preferably those with a higher fibre content, such as pomegranate, physalis, pear, kiwi, raspberry, gooseberry, redcurrants, blueberry.

CONFIDENTIAL 49 (92)

Clinical Study Protocol EP-002 Final version v3.0 12NOV2020

- If eating soup, take medication together with a piece of bread before starting to eat soup.
- Consumption of meal items containing saccharose or easily digestible starch should be minimised, such as candy, chocolate, chips, cheese doodles, cookies, cakes, ice-cream, soda, ready-made mashed potatoes, white low-fibre bread, fruit yoghurt.
- No restriction on coffee or tea. The consumption of hot non-caloric beverages is encouraged.
- Water is the preferred drink.
- Eat regular meals and avoid snacking, with the exception of fresh fruits/berries and small servings of nuts if meals are delayed.
- Choose dietary fat sources that contain a high proportion of calcium, such as hard cheese, brie, halloumi, feta cheese, pesto, sardines in oil.
- Consumption of meal items containing a high amount of dietary fat should be minimised, such as large servings of pizza, certain fast foods, chips and other fried potato products.

9.6.2 Prior and concomitant therapy

Regular use of medication listed in Table 9.6-1 is prohibited during the study, from 2 weeks prior to IMP administration until Visit 6.

Table 9.6-1 Prohibited medication

Type of medication	ATC code	Examples (list is not exhaustive)
Drugs that are affected by or that affect orlistat and acarbose		Cyclosporin, amiodarone, anti-epileptic drugs, benzodiazepines, anti-psychotic drugs, anti-depressants (stable treatment for more than 2 months prior to first dose of IMP is allowed), cholestyramine, coal tar, digestive products including enzymes, digoxin, anticoagulants (warfarin)
Drugs altering glucose metabolism and drugs used for diabetes	A10A A10B	Insulin, metformin, glibenclamide
Over-the-counter fat or carbohydrate uptake blockers		Glucosanol, Liposanol, XLS Medical fat binder, Bantaxin, green coffee
Antacids, proton pump inhibitors,	A02A	Samarin, Novalucol and other antacids
Histamine (H2)-receptor antagonists, prostaglandin analogues and other drugs that enhance mucosal defence and/or control reflux	A02BC	Losec (omeprazole), Nexium (omeprazole), Nixacid (lansoprazole), pantoprazole, and other proton pump inhibitors (PPIs)
and, of control 101101.		Tagamet (cimetidine)
	A02BX02	Andapsin (sucralfate)
	G02AD06	Arthrotec (misoprostol)

Other medications considered necessary for the patient's safety and wellbeing may be given at the discretion of the Investigator. Following consultation with the Sponsor, the Investigator will determine whether or not the patient can continue in the study.

CONFIDENTIAL 50 (92)

9.7 **Screen failures**

Screen failures are defined as patients who consent to participate in the clinical study but are not subsequently randomised in the study. A minimal set of screen failure information is required to ensure transparent reporting of screen failure patients. Minimal information includes documentation of signed and dated informed consent form (ICF) and reason(s) for screening failure.

Re-screening can be performed once if any of the following were reasons for screening failure or non-randomisation (as judged by the Investigator):

- Practical reasons.
- Non-significant medical conditions (e.g. influenza, nasopharyngitis).
- Plasma or blood donation outside allowed time windows.

For patients who are re-screened, a new screening number will be assigned and a new, signed ICF will be collected.

9.8 **Patient withdrawal**

9.8.1 General withdrawal criteria

Patients are free to discontinue their participation in the study at any time and for whatever reason without affecting their right to an appropriate follow-up investigation or their future care. The reason for withdrawal of consent should be documented.

Patients may be discontinued from the study at any time at the discretion of the Investigator.

Reasons for discontinuation include:

- Patient withdrawal of consent
- Severe non-compliance to study protocol procedures, as judged by the Investigator. and/or Sponsor
- Patient is lost to follow-up.
- Significant AEs posing a risk for the patient, as judged by the Investigator and/or Sponsor
- Pregnancy
- Death
- Meeting of an exclusion criterion during the study, which, in the opinion of the Investigator, may pose a risk for the patient

9.8.2 Liver chemistry withdrawal criteria

Liver chemistry threshold stopping criteria have been designed to assure patient safety and to evaluate liver event aetiology. Study treatment will be stopped for the individual patient if any

CONFIDENTIAL 51 (92)

of the following liver chemistry stopping criteria, defined in the U.S. Food and Drug Administration (FDA) Guidance on Drug-Induced Liver Injury [34] is met:

• ALT 3 x Upper Limit of Normal (ULN) and total bilirubin $\ge 2x$ ULN (>35% direct bilirubin); **or** ALT 3xULN and INR > 1.5)

NOTE: plasma bilirubin fractionation will be performed.

- ALT 5xULN.
- ALT 3xULN if associated with symptoms (new or worsening) believed to be related to hepatitis (such as fatigue, nausea, vomiting, right upper quadrant pain or tenderness or jaundice) or believed to be related to hypersensitivity (such as fever, rash or eosinophilia).
- Patients with ALT 3xULN and < 5xULN and bilirubin < 2xULN, who do not exhibit hepatitis symptoms or rash, will be allowed to continue study treatment as long as their liver status is monitored weekly for 4 weeks.

If ALT is still $\geq 3xULN$ after 4 weeks of continued treatment, the treatment will be stopped. Approximately 4 weeks after stop of treatment, subjects will be scheduled for an safety follow-up visit (corresponding to Visit 6) for follow-up safety assessments including safety laboratory sampling.

In case the liver enzyme parameters have not returned to baseline levels at the safety follow-up visit (2 weeks after end of treatment), subjects will be referred to their general practitioner for continued follow-up by standard medical/clinical care.

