	Prior and concomitant med.	11.3.5				X			

CSP=Clinical study protocol, HIV=Human immunodeficiency virus.

- 1. For detailed schedule of events, see Table 8.1-4.
- 2. At Visit 6 or after early withdrawal.
- 3. Women of child-bearing potential (WOCBP) only, urine test.
- 4. Drug tests may also be performed at additional random occasions during the study.
- 5. Full safety laboratory profile: Clinical chemistry, haematology, coagulation, urinalysis (dip stick). Fasting is not required prior to Visit 1 and Visit 6.

6. Liver enzymes: ALT, AST, ALP, GGT.

CONFIDENTIAL 39 (92)

Clinical Study Protocol EP-002 Final version v3.0 12NOV2020

- 7. Visit 5: steady-state sample pre-dose.
- 8. To be filled in by the patient during, before or after the visits, and at the end of week 2, week 4, and week 8 to follow GI symptoms during the run-in phase.
- 9. To be filled in by the patient before breakfast (at the clinic), then once every hour until lunch (at home).
- 10. To be filled in by the patient at any hour on the day of Visit 2, and at Visit 5 at approximately the same hour (± 1h) as was done at Visit 2.
- 11. IMP administration at the clinic as follows:
 - Visit 2: Placebo capsule during breakfast at the clinic, first randomised IMP dose during lunch at home.
 - Visit 3 and Visit 4: IMP dose during breakfast at the clinic.
 - Visit 5: Last IMP dose during breakfast at the clinic.
- 12. Breakfast at the clinic after weight-related assessments and blood sampling. IMP taken during breakfast.
- 13. Visit 7 applicable for patients giving their separate consent to participate in the follow-up visit.
- 14. New Informed consent required before 6 months follow-up visit. Consent may be collected at any time point prior to any study assessments at Visit 7.
- 15. Visit 7: HbA1c only
- 16. Visit 7: blood pressure only

CONFIDENTIAL 40 (92)

Clinical Study Protocol EP-002 Final version v3.0 12NOV2020

Table 8.1-4 Detailed schedule of events for Visit 2 to 5

Category	Visit	Refer to									Visit 3	3 to 5			
		CSP Section	A	t the clini	ic		At home		At	At the clinic			At home		
	Assessment		Before breakfast	00:00	01.00	02:00	03:00	04:00	Before breakfast	00:00	01.00	02:00	03:00	04:00	
Screening and	Incl./excl. criteria	11.3.2	X												
demographics assessments	Brief physical examination	11.6.2.2	X						X						
	Alcohol breath test	11.3.7	X						X						
	Pregnancy test ¹	11.3.8	X						X						
Weight-related	Weight	11.4.1	X						X						

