11.6.5 Safety laboratory assessments

Blood samples for analysis of clinical chemistry, haematology and coagulation parameters will be collected through venepuncture and sent to the certified local laboratory at Uppsala University Hospital and/or Linköping and analysed by routine analytical methods.

Urine analysis will be performed at each research clinic using dip sticks. The assessments will be performed at visits specified in Table 8.1-3.

Urine pregnancy tests will be performed at visits specified in Table 8.1-3.

The safety laboratory parameters are defined in Table 11.6-1 (full safety laboratory) and Table 11.6-2 (liver function only), and will be assessed at time-points detailed in Table 8.1-3.

Abnormal values assessed by the Investigator as clinically significant will be reported as AEs. If an abnormal value is associated with corresponding clinical signs or symptoms, the sign/symptom should be reported as the AE.

CONFIDENTIAL 68 (92)

Clinical Study Protocol EP-002 Final version v3.0 12NOV2020

Table 11.6-1 Safety laboratory parameters

Category	Parameter
Clinical chemistry	ALT
,	Albumin
	ALP
	AST
	Bilirubin (total and conjugated)
	Calcium
	Creatinine
	GGT
	Glucose
	Hb1Ac ¹
	Phosphate
	Potassium
	Sodium
	Urea
Haematology	Haematocrit
	Haemoglobin (Hb)
	Platelet count
	Red blood cell (RBC) count
	White blood cell (WBC) count with differential count
Coagulation	Activated Partial Thromboplastin Time (APTT)
	Prothrombin Complex International Normalised Ratio (PK[INR])
Urinalysis (dip stick)	Erythrocytes
J \ 1 /	Glucose
	Ketones
	Leucocytes
	Nitrite
	pH
	Protein
	Specific gravity
	Urobilinogen
FSH-test	FSH ²
Pregnancy test	Urine pregnancy test ³
	crime programme, test

CONFIDENTIAL 69 (92)

¹HbA1c at screening only
² At screening, post-menopausal females only, as applicable
³ WOCBP only

Table 11.6-2 Liver function parameters

Category	Parameter
Clinical chemistry	ALT
	ALP
	AST
	GGT

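### Protocol 9.8.2: the liver continuation rule omits INR, so a patient with ALT from 3 to below 5xULN and INR above 1.5 meets both a mandatory stop and the permission to continue

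*Protocol*

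**What the plan says.** Protocol section 9.8.2 opens with a mandatory rule: "Study treatment will be stopped for the individual patient if any" of the listed criteria is met. For a patient whose ALT is at least 3xULN, the criteria are:

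- total bilirubin at least 2xULN with a direct fraction above 35%, or, as an alternative, "ALT 3xULN and INR > 1.5";
- ALT 5xULN;
- new or worsening symptoms thought to reflect hepatitis, or symptoms "believed to be related to hypersensitivity (such as fever, rash or eosinophilia").

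The final bullet of the same list is a permission. Its laboratory range is "Patients with ALT 3xULN and < 5xULN and bilirubin < 2xULN". Within that range, the bullet says that those "who do not exhibit hepatitis symptoms or rash, will be allowed to continue study treatment". The only further proviso concerns follow-up: they may do so "as long as their liver status is monitored weekly for 4 weeks". The section then adds that treatment stops if ALT is still at least 3xULN after those 4 weeks.

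On laboratory testing, section 11.6.5 distinguishes "Table 11.6-1 (full safety laboratory) and Table 11.6-2 (liver function only), and will be assessed at time-points detailed in Table 8.1-3". The short liver panel is ALT, AST, ALP and GGT. Bilirubin, INR and the differential white cell count belong to the full panel. Table 8.1-3 places the short panel at Visits 2 to 5, and the full panel at screening and at the safety follow-up (footnote 2: "At Visit 6 or after early withdrawal").

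**The concern.** A rule for continuing should apply only to patients whom the stop rules leave untouched. This one does not. It repeats the bilirubin and hepatitis-symptom conditions but leaves out INR, which is a stop condition in its own right. For hypersensitivity it names only rash.

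Section 6.3 gives rare liver effects of acarbose as the reason for liver sampling, and 9.8.2 is the only liver-specific stopping rule. A site with a patient in the 3 to 5xULN band is likely to turn to the continuation bullet, because it is the sentence written for that band. Every condition in that bullet can be satisfied without an INR result. The weekly check does not clearly close the gap: 9.8.2 does not list the tests that make up liver status, and the protocol's own short liver panel contains no INR. What is at stake is that two sites could treat the same patient differently, each able to cite 9.8.2.

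**Working it through.** The protocol gives no figure for this point, so the check compares the two rules in 9.8.2 condition by condition. The text shows ALT 3xULN without a comparator. It is read here as ≥, since the sign was probably lost in text extraction.

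**Step 1. Conditions side by side, for ALT ≥3 and <5xULN**

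| Stop criterion | Excluded by the continuation bullet? |
|---|---|
| Bilirubin ≥2xULN with >35% direct | Yes (requires bilirubin <2xULN) |
| INR >1.5 | No |
| Symptoms believed due to hepatitis | Yes |
| Signs believed due to hypersensitivity | Rash only |

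**Step 2. One worked case.** ALT 4xULN, bilirubin 1xULN, INR 1.6, no symptoms, no rash.

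- Stop: ALT 4 ≥ 3 and INR 1.6 > 1.5, so the stop rule is met.
- Continue: 3 ≤ 4 < 5, bilirubin 1 < 2, no hepatitis symptoms, no rash, so the permission applies.

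Reading the comparator as > changes nothing here, because 4 lies inside the band either way. The layout of the bullets does not matter either.

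**Step 3. Enumeration.** Both rules were coded and run over ALT 3, 4, 4.9 xULN; bilirubin 1, 1.9, 2, 3 xULN; direct fraction 20%, 50%; INR 1.0, 1.5, 1.6, 2.0; and yes/no for hepatitis symptoms, rash, and another hypersensitivity sign.

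- Combinations: 3 × 4 × 2 × 4 × 2 × 2 × 2 = 768.
- Continuation met: 3 (ALT) × 2 (bilirubin <2) × 2 (direct fraction) × 4 (INR) × 2 (other sign) = 96.
- Of those, no stop criterion met: 3 × 2 × 2 × 2 (INR ≤1.5) × 1 (no other sign) = 24.
- Both rules met: 96 − 24 = 72. These are 24 from INR alone, 24 from INR together with another hypersensitivity sign, and 24 from the other sign alone.
- Adding INR ≤1.5 to the continuation rule leaves 24. Also adding no hypersensitivity signs leaves 0.
- Neither rule met: 3 (ALT) × 2 (bilirubin ≥2) × 1 (direct 20%) × 2 (INR ≤1.5) × 1 (no symptoms or signs) = 12. These are patients with bilirubin ≥2xULN and a direct fraction of 35% or less.

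The counts depend on the grid values chosen. They show which text conditions collide and that the repair removes the collision. They say nothing about how often patients would be affected.

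**Step 4. Schedule.** Of the visits with the short liver panel (2, 3, 4, 5), three fall on randomised drug: 3, 4 and 5. INR is scheduled at 0 of these 3, and so is bilirubin. Visit 5 is the day of the last dose, so the rule can alter treatment mainly after Visits 3 and 4.

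**The case against.** The strongest reply is that the operative rule is clear enough. The stem is mandatory and is triggered by any single criterion, INR above 1.5 is named in the first one, and the continuation bullet is only a permission that comes after the stop criteria. Read together, the stop prevails. This largely stands: it is the most natural reading. It does not remove the defect, because 9.8.2 states no precedence and the permission is the more specific text for the band.

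The hypersensitivity overlap is weaker still. It arises only if an investigator already believes that the sign reflects hypersensitivity, which meets an explicit stop criterion, and then continues because the sign was not a rash. Rash can fairly be read as shorthand. This objection stands, and the point should rest on INR.

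There are also backstops. Continuation requires weekly monitoring, treatment stops if ALT has not fallen below 3xULN after 4 weeks, clinically significant laboratory values are reported as adverse events (11.6.5), and the investigator may discontinue a patient at any time (9.8.1). These limit the consequence and are accepted.

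A reader might infer from the schedule that INR goes unmeasured when it matters, or that the visit panels are deficient. The protocol does not support that. Applying the INR stop criterion already requires an INR once ALT reaches 3xULN, and bilirubin is equally absent from Visits 3 to 5. The schedule shows only that nothing in the continuation bullet prompts the test.

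**Conclusion.** The contradiction is real and should be corrected. Within ALT ≥3 and <5xULN, with bilirubin <2xULN and no hepatitis symptoms or rash, an INR above 1.5 satisfies both a mandatory stop and a permission to continue, and no precedence is written. Hypersensitivity signs other than rash share the slip as a minor second case. In the other direction, bilirubin ≥2xULN with ≤35% direct, INR ≤1.5 and no symptoms falls under neither rule.

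A reader might go further and conclude that patients will be kept on drug against a stop criterion, or that harm is to be expected. The documents do not support either: the stopping stem most naturally governs, the backstops apply, and no event rate is given from which to estimate a frequency. No endpoint or efficacy analysis is shown to be affected.

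The conclusion rests on the wording of 9.8.2 as supplied. It does not depend on whether the ALT comparator is > or ≥.

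**What to change.** Move the continuation sentence out of the stop list, place it after the list, and word it along these lines:

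*Patients with ALT ≥3xULN and <5xULN who meet none of the stopping criteria above, and who have bilirubin <2xULN, INR ≤1.5 and no new or worsening symptoms believed related to hepatitis or hypersensitivity, may continue with weekly liver monitoring (including bilirubin and INR) for 4 weeks; any stopping criterion takes precedence.*

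The conditions must be cumulative. Meeting none of the stopping criteria is not the same as bilirubin <2xULN, because the bilirubin criterion also needs a direct fraction above 35%. A wording that treats the two as equivalent would contradict itself for a patient with bilirubin ≥2xULN and ≤35% direct.

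Add a separate sentence saying what happens to that patient when no stop criterion is met. Whether to stop, or to continue under closer monitoring, is a clinical decision for the sponsor and the investigator.

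Numeric thresholds and scheduled visits do not change. The cost is a protocol wording change plus bilirubin and INR at the weekly checks, confined to patients in this ALT band. The INR when ALT first reaches 3xULN is already implied by the existing stop criterion.

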9.8.3 Procedures for discontinuation of a patient from the study

A patient who prematurely discontinues participation in the study will always be asked about the reason(s) for discontinuation and the presence of any AEs. If a patient withdraws consent, the Investigator must ask the patient if he/she is willing, as soon as possible, to be assessed according to the procedures scheduled for the safety follow-up visit (Visit 6). Any ongoing AEs will be followed as described in Section 11.6.1.15.

The primary reason for discontinuation/early withdrawal must be specified in the eCRF and final drug accountability must be performed.

9.11 Emergency unblinding during the study

The treatment code may only be broken by the Principal Investigator or delegate in case of emergency when knowledge of the treatment received is necessary for the proper medical management of the patient. The code breaking procedure should be carefully documented.

For unblinding procedures in case of a potential suspected unexpected serious adverse reaction (SUSAR), refer to Section 11.6.1.14.

10 TREATMENTS

10.1 Identity of investigational medicinal products

The drug product, EMP16-02, is an FDC that contains two active pharmaceutical ingredients (API):

- Orlistat (CAS No. 96829-58-2)
- Acarbose (CAS No. 56180-94-0)

The IMP is supplied as oral MR capsules in two different strengths:

- 60 mg orlistat/20 mg acarbose
- 90 mg orlistat/30 mg acarbose'

EMP16-02 capsules are composed of three pharmaceutical fractions (granules denoted G1, G2 and G3) of multiple unit pellets with different release rates and amounts of orlistat and acarbose. The EMP16-02 capsules with highest strength (90 mg/30 mg) are composed of the following fractions:

- 1. A granule fraction (G1) with a prolonged release of 18 mg acarbose, which is designed to release acarbose with a delayed on-set of 30 minutes after oral intake in fed state, and a subsequent extended release phase of 4-5 hours.
- 2. An enteric-coated granule fraction (G2) containing 65 mg orlistat and 12 mg acarbose, which is designed to initiate a rapid release of orlistat and acarbose once the formulation parts have been emptied into the almost neutral luminal conditions (pH around 6.5) in the proximal small intestine [35].

CONFIDENTIAL 53 (92)

Clinical Study Protocol EP-002 Final version v3.0 12NOV2020

3. A third fraction (G3) containing 25 mg orlistat with a delayed on-set release mechanism of 30 minutes after oral intake in the fed state, and a subsequent extended release phase of 4-5 hours.

The average size distributions of the pellet fractions G1, G2 and G3 are below 700 µm to be emptied from the stomach uniformly during the post-prandial phase [36,37].

EMP16-02 capsules are supplied in plastic bottles.

Placebo capsules are identical in appearance but contain only cellulose.

